6.3 Secondary Endpoints

Measure progression free survival (PFS) and clinical benefit rate (CBR) to the combination of guadecitabine and pembrolizumab.

PFS will be defined as the time from first dose of study treatment until disease progression or death from any cause. Any patient who has completed at **least 1 cycle of treatment** will be evaluable for PFS endpoint.

Clinical Benefit Rate(CBR) will be defined as patients with CR + PR or SD (SD for at least 3 months). Any patient who has completed at **least 2 cycles of treatment** will be evaluable for CBR endpoint.

Measure toxicity profiles for the combination of guadecitabine and pembrolizumab. The number, type, grade, severity, and frequency of adverse events will be tabulated; adverse events are assessed at least once per cycle. Any patient who receives **at least one dose** of study therapy will be evaluable for toxicity endpoints.

Measure objective response rate (ORR) to the combination of guadecitabine and pembrolizumab using the Immune Related Response Criteria (irRC)
(Note: Response assessments will be made both using the irRC, and using RECIST v1.1, allowing additional comparisons among these criteria for disease response assessment. Measurable and non-measurable lesions will be followed by both RECIST v1.1 & irRC. Disease progression will be determined using RECIST 1.1 criteria).

6.4 Exploratory Objectives:

To test the hypothesis that the combination of guadecitabine and pembrolizumab reactivates immune responses by allowing re-expression of tumor antigens silenced epigenetically, we will measure several endpoints:

- NY-ESO-1 and MAGE antigens' promoter methylation (pyrosequencing) and mRNA expression levels (quantitative RT-PCR) will be measured before and after treatment in *DNA (plasma and/or tumor biopsies)* and *RNA (tumor biopsies)*, respectively.
- Cytokine response (IFN γ , IL2, IL6, IL10, TNF α) will be measured in plasma by ELISA.
- Measure LINE 1 methylation in DNA extracted from PBMCs (D5 vs. D1 of cycles

NU Study Number: NU 16G03
Merck Study Number: 3475-244

1 and 2).

- Expression of the PD-L1 ligand will be measured by IHC in archival tumors.
- Tumor infiltrating lymphocytes (TILs) will be quantified in tumor biopsies before and after treatment (IHC).

All biological parameters will be correlated with clinical endpoints (ORR and PFS).

6.5 Immune Related Response Criteria (irRC)

6.5.1 Summary of irRC

This study will evaluate concordance of the Immune Related Response Criteria (irRC) with RECISTv 1.1 and OS. These response criteria were developed to overcome the variable and unusual patterns of response to immunotherapeutic agents, in particular, ipilimumab [34]. The development of the guidelines were prompted by observations, mostly in subjects with metastatic melanoma, of initial disease progression followed by later response, late responses, and mixed responses with an overall decrease in tumor burden.

6.5.2 Antitumor response based on total measurable tumor burden:

For the irRC, only index and measurable new lesions are taken into account (in contrast to conventional WHO criteria, which do not require the measurement of new lesions, nor do they include new lesion measurements in the characterization of evolving tumor burden). At the baseline tumor assessment, the sum of the products of the two largest perpendicular diameters (SPD) of all index lesions (5 lesions per organ, up to 10 visceral lesions) is calculated. At each subsequent tumor assessment, the SPD of the

index lesions and of new, measurable lesions (up to 5 new lesions per organ; 10 visceral lesions) are added together to provide the total tumor

burden: Tumor Burden = $SPD_{\text{index lesions}} + SPD_{\text{new, measurable lesions}}$

Table 5: Comparison of WHO and irRC criteria:

	WHO	irRC
New, measurable lesions	Always represent PD	Incorporated into tumor burden
New, non-measurable lesions	Always represent PD	Do not define progression (but preclude irCR)
Non-index lesions	Changes contribute to defining BOR of CR, PR, SD, and PD	Contribute to defining irCR (complete disappearance required)
CR	Disappearance of all lesions in two consecutive observations not less than 4 wk apart	Disappearance of all lesions in two consecutive observations not less than 4 wk apart
PR	≥50% decrease in SPD of all index lesions compared with baseline in two observations at least 4 wk apart, in absence of new lesions or unequivocal progression of non-index lesions	≥50% decrease in tumor burden compared with baseline in two observations at least 4 wk apart

NU Study Number: NU 16G03
Merck Study Number: 3475-244

SD	50% decrease in SPD compared with baseline cannot be established nor 25% increase compared with nadir, in absence of new lesions or unequivocal progression of non-index lesions	50% decrease in tumor burden compared with baseline cannot be established nor 25% increase compared with nadir
PD	At least 25% increase in SPD compared with nadir and/or unequivocal progression of non-index lesions and/or appearance of new lesions (at any single time point)	At least 25% increase in tumor burden compared with nadir (at any single time point) in two consecutive observations at least 4 wk apart

6.5.3 Time-Point Response Assessment Using irRC:

Percentage changes in tumor burden per assessment time point describe the size and growth kinetics of both conventional and new, measurable lesions as they appear. At each tumor assessment, the response in index and new, measurable lesions is defined based on the change in tumor burden (after ruling out irPD). Decreases in tumor burden must be assessed relative to baseline measurements (i.e., the SPD of all index lesions at screening). The irRC were derived from WHO criteria and, therefore, the thresholds of response remain the same. However, the irRC response categories have been modified from those of WHO criteria as detailed above.

6.5.4 Overall Response Using irRC:

The sum of the products of diameters at tumor assessment using the immune-related response criteria (irRC) for progressive disease incorporates the contribution of new measurable lesions. Each net Percentage Change in Tumor Burden per assessment using irRC criteria accounts for the size and growth kinetics of both old and new lesions as they appear.

6.5.5 Definition of Index Lesions Response Using irRC

- irComplete Response (irCR): Complete disappearance of all *index* lesions. This category encompasses exactly the same subjects as "CR" by the mWHO criteria.
- irPartial Response (irPR): Decrease, relative to baseline, of 50% or greater in the sum of the products of the 2 largest perpendicular diameters of all *index* and all new measurable lesions (i.e., Percentage Change in Tumor Burden). **Note:** the appearance of new measurable lesions is factored into the overall tumor burden, but does not automatically qualify as progressive disease until the SPD increases by \geq 25% when compared to SPD at nadir.
- irStable Disease (irSD): Does not meet criteria for irCR or irPR, in the absence of progressive disease.
- irProgressive Disease (irPD): At least 25% increase Percentage Change in Tumor Burden (i.e., taking sum of the products of all *index* lesions and any new lesions) when compared to SPD at nadir.

6.5.6 Definition of Non-Index Lesions Response Using irRC

- irComplete Response (irCR): Complete disappearance of all *non-index* lesions. This category encompasses exactly the same subjects as "CR" by the mWHO criteria.
- irPartial Response (irPR) or irStable Disease (irSD): *non-index* lesion(s) are not considered in the definition of PR, these terms do not apply.
- irProgressive Disease (irPD): Increases in number or size of non-index

NU Study Number: NU 16G03

Merck Study Number: 3475-244

lesion(s) does not constitute progressive disease unless/until the Percentage Change in Tumor Burden increases by 25% (i.e., the SPD at nadir of the index lesions increases by the required amount).

6.5.7 Impact of New Lesions on irRC

New lesions in and by themselves do not qualify as progressive disease. However, their contribution to total tumor burden is included in the SPD, which in turn feeds into the irRC criteria for tumor response. Therefore, new non-measurable lesions will not discontinue any subject from the study.

6.5.8 Definition of Overall Response Using irRC

Overall response using irRC will be based on these criteria:

- *Immune-Related Complete Response (irCR):* Complete disappearance of *all* tumor lesions (index and non-index together with no new measurable/unmeasurable lesions) for at least 4 weeks from the date of documentation of complete response.
- *Immune-Related Partial Response (irPR):* The sum of the products of the two largest perpendicular diameters of all index lesions is measured and captured as the SPD baseline. At each subsequent tumor assessment, the sum of the products of the two largest perpendicular diameters of all index lesions and of new measurable lesions are added together to provide the Immune Response Sum of Product Diameters (irSPD). A decrease, relative to baseline of the irSPD compared to the previous SPD baseline, of 50% or greater is considered an immune Partial Response (irPR).
- *Immune-Related Stable Disease (irSD):* irSD is defined as the failure to meet criteria for immune complete response or immune partial response, in the absence of progressive disease.
- *Immune-Related Progressive Disease (irPD):* It is recommended in difficult cases to confirm PD by serial imaging. Any of the following will constitute progressive disease:
 - At least 25% increase in the sum of the products of all index lesions over nadir SPD calculated for the index lesions.
 - At least a 25% increase in the sum of the products of all index lesions and new measurable lesions (irSPD) over the baseline SPD calculated for the index lesions.

6.5.9 Immune-Related Best Overall Response Using irRC (irBOR):

irBOR is the best confirmed irRC overall response over the study as a whole, recorded between the date of first dose until the last tumor assessment before subsequent therapy (except for local palliative radiotherapy for painful bone lesions) for the individual subject in the study. For the assessment of irBOR, all available assessments per subject are considered.

irCR or irPR determinations included in the irBOR assessment must be confirmed by a second (confirmatory) evaluation meeting the criteria for response and performed no less than 4 weeks after the criteria for response are first met.

Derivation of irRC overall responses:

Measurable response	Nonmeasurable response		Overall response
Index and new, measurable lesions (tumor burden), %	Non-index lesions	New, nonmeasurable lesions	Using irRC
↓100	Absent	Absent	irCR ^t
↓100	Stable	Any	irPR ^t
↓100	Unequivocal progression	Any	irPR ^t
↓≥50	Absent/Stable	Any	irPR ^t
↓≥50	Unequivocal progression	Any	irPR ^t
↓<50 to <25↑	Absent/Stable	Any	irSD
↓<50 to <25↑	Unequivocal progression	Any	irSD
≥25	Any	Any	irPD ^t

*Decreases assessed relative to baseline (scan prior to start of any protocol therapy), including measurable lesions only

^tAssuming response (irCR) and progression (irPD) are confirmed by a second, consecutive assessment at least 4 wk apart.

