Measurable disease per RECIST 1.1 is defined as the presence of at least one measurable lesion. Measurable lesions are defined as those that can be accurately measured in at least one dimension (longest diameter to be recorded) as ≥ 20 mm by chest x-ray, as ≥ 10 mm with CT scan, or ≥ 10 mm with calipers by clinical exam. For irRC, measurable lesions are defined as those that can be accurately measured in at least two dimensions as 10x10mm with CT scan. All tumor measurements must be recorded in millimeters (or decimal fractions of centimeters).

Malignant Lymph Nodes

To be considered pathologically enlarged and measurable, a lymph node must be ≥ 15 mm in short axis when assessed by CT scan (CT scan slice thickness recommended to be no greater than 5 mm). At baseline and in follow-up, only the short axis will be measured and followed.

NU Study Number: NU 16G03
Merck Study Number: 3475-244

Non-measurable Lesions

For both RECIST 1.1 and irRC, all other lesions (or sites of disease), including small lesions (longest diameter <10 mm or pathological lymph nodes with ≥ 10 to <15 mm short axis), are considered non-measurable disease. Bone lesions, leptomeningeal disease, ascites, pleural/pericardial effusions, lymphangitis cutis/pulmonitis, inflammatory breast disease, and abdominal masses (not followed by CT or MRI), are considered as non-measurable.

Note: *Cystic lesions that meet the criteria for radiographically defined simple cysts should not be considered as malignant lesions (neither measurable nor non-measurable) since they are, by definition, simple cysts. 'Cystic lesions' thought to represent cystic metastases can be considered as measurable lesions, if they meet the definition of measurability described above. However, if non-cystic lesions are present in the same subject, these are preferred for selection as target lesions.*

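### The irRC progression rule differs between Table 5/6.5.5 and 6.5.8, and the short-axis-only rule for nodes cannot supply the two-diameter product that irRC needs

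*Combined protocol and SAP*

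**What the plan says.** **Progression, Table 5 (6.5.2).** irPD is "At least 25% increase in tumor burden compared with nadir (at any single time point) in two consecutive observations at least 4 wk apart". Tumor burden is defined just above the table as index plus new measurable lesions.

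**Progression, 6.5.5.** The same comparison: the sum over index "lesions and any new lesions) when compared to SPD at nadir". A new measurable lesion "does not automatically qualify as progressive disease until the SPD increases by" 25% or more from nadir. Section 6.5.6 also refers to nadir.

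**Progression, 6.5.8.** This section defines overall response. It gives two bullets, either of which is enough for irPD. The first takes index lesions alone and uses their nadir as the reference. The second is the only one that counts new lesions, and it sets them against the starting value: "At least a 25% increase in the sum of the products of all index lesions and new measurable lesions (irSPD) over the baseline SPD".

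**Confirmation.** Table 5 and the footnote to the derivation table (end of 6.5.9) both require a second consecutive assessment at least 4 weeks apart. Section 6.5.8 says: "It is recommended in difficult cases to confirm PD by serial imaging".

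**Derivation table.** Its footnote fixes baseline as the reference for decreases. It gives no reference for the row that assigns irPD at 25% or more.

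**Nodes, 6.1.** For malignant lymph nodes, "only the short axis will be measured and followed", at baseline and afterwards. The paragraph does not limit this to RECIST 1.1. The same section requires two dimensions for an irRC measurable lesion, and 6.5.2 builds burden from products of two perpendicular diameters.

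**The concern.** Two careful readers can follow different paragraphs of 6.5 and classify the same scan differently. The sharpest conflict is over new lesions: Table 5 and 6.5.5 add them to the burden that is compared with nadir, whereas 6.5.8 lets them count only against baseline. After any shrinkage those two references separate. Nothing in the protocol says which section prevails.

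Two uses of the irRC data are exposed. Objective response by irRC is a listed secondary endpoint (2.2.4, 6.3), to be estimated under 10.3.2. Section 6.5.1 also says that the study will examine how irRC agrees with RECIST 1.1 and overall survival, and that depends on irSD and irPD labels as well as on responses.

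The node wording raises a separate question. One axis does not give a product of two diameters, so a nodal lesion cannot enter the irRC sum as defined unless the reader improvises.

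**Working it through.** The plan states no sample size, power or rate for the irRC endpoint, so there is no figure to reproduce. The check applies the written rules to example scans.

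**Rules**, with baseline burden set to 100 and, in the table, no new lesions at the nadir scan:
- T (Table 5, 6.5.5): index + new ≥ 1.25 × nadir total.
- S1 (6.5.8, first bullet): index ≥ 1.25 × nadir index.
- S2 (6.5.8, second bullet): index + new ≥ 1.25 × baseline = 125.
- irPR size (Table 5, 6.5.5, 6.5.8): index + new ≤ 50.

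| Scan | Nadir | Index | New | Total | Total vs nadir | Total vs baseline | T met | S1 or S2 met | irPR size |
|---|---|---|---|---|---|---|---|---|---|
| A | 60 | 60 | 20 | 80 | +33% | −20% | yes | no | no |
| B | 40 | 40 | 45 | 85 | +112.5% | −15% | yes | no | no |
| C | 30 | 30 | 10 | 40 | +33% | −60% | yes | no | yes |
| D | 20 | 40 | 0 | 40 | +100% | −60% | yes | yes (S1) | yes |

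Scans A and B move between irSD and irPD, and neither label is a response. Scan C is the kind that could touch the response rate. In scan D the sections agree, because regrowth of index lesions is caught by S1.

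**How far the thresholds separate.** Growth driven by new lesions needs 1.25 × nadir under T and 125 ÷ nadir under S2:
- nadir 50: 1.25 × against 125/50 = 2.5 × nadir;
- nadir 30: 1.25 × against 125/30 = 4.17 × nadir.

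**When the response rate is at stake.** A scan must meet a progression threshold and still be of irPR size. Under T, 1.25 × nadir ≤ 50 gives nadir ≤ 40. The same bound holds for S1, because the index sum cannot exceed the total. S2 needs a total of at least 125 and so can never coincide with irPR size. A nadir of 50 is therefore a case where the thresholds differ widely but no response is at stake.

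**The reverse disagreement.** Take a nadir of index 100 + new 200 = 300, then index 130 + new 170 = 300, with an assumed baseline of 400. S1 is met (+30%). T is not (0%), nor is S2 (300 < 1.25 × 400 = 500). Correcting only the second bullet would leave this conflict in place.

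**Nodes (assumed sizes).** A node shrinks from 30×20 mm to 24×12 mm:
- product: 1 − (24×12)/(30×20) = 1 − 288/600 = 52% decrease, irPR size;
- short axis: 1 − 12/20 = 40% decrease, not irPR size;
- short axis squared: 1 − 144/400 = 64% decrease.

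**Size per patient.** Assuming the irRC rate uses the 35 evaluable patients, one reclassified response is 1/35 = 2.9 percentage points.

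**The case against.** A reader might infer that the irRC response rate as a whole depends on which progression paragraph is applied. The documents do not support that. irPR has a single reference, a 50% decrease from baseline, wherever it is defined. Section 6.5.9 builds best response from all available assessments before subsequent therapy and is not stated to stop at irPD, so a later qualifying scan can still confirm irPR. A single scan such as C is also only unconfirmed irPD under Table 5. This objection stands, and it confines the effect on the response rate to the narrow case derived above.

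A reader might also say that the baseline bullet does not replace nadir, because it is an alternative to a nadir bullet in the same list. That is right for index lesions. It does not help when growth comes from new lesions, because the nadir bullet leaves them out.

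Precedence of progression over response is not missing: 6.5.3 assigns response only after irPD has been ruled out. The derivation table simply does not repeat it.

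On nodes, a reader might conclude that patients with mainly nodal disease have no computable irRC burden. That goes too far. The irRC text asks for two dimensions, and the node paragraph may be RECIST wording whose scope was left unstated. The documents do not say how many patients have mainly nodal disease. What remains is an unrestricted short-axis instruction that conflicts with the irRC definition.

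**Conclusion.** The contradictions are real as written: whether new lesions are compared with nadir or baseline, whether irPD must be confirmed, and how nodes enter the irRC sum. The baseline bullet in 6.5.8 is the outlier; Table 5, 6.5.5, 6.5.6 and the first bullet of 6.5.8 all use nadir.

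The progression conflict mainly shifts patients between irSD and irPD, and so bears on the concordance with RECIST 1.1 and overall survival. It changes the irRC response rate only if the scan needed to confirm irPR is at least 25% above a nadir at or below 40% of baseline. The node conflict can change irPR directly. The documents give no basis for estimating how many patients either would affect; 2.9 points per patient is a unit, not a forecast. Nor do they support attributing every difference between RECIST and irRC results to the choice of rule.

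Severity is minor to moderate. The endpoint is secondary and only estimated. Progression in the trial is determined by RECIST 1.1 (6.1, 6.3), so the primary response rate, PFS and the two-stage design are untouched.

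**What to change.** - In 6.5.8, replace both irPD bullets and the sentence on difficult cases with one rule that matches Table 5: total burden (index plus new measurable lesions) at least 25% above nadir total burden, confirmed by a second consecutive assessment at least 4 weeks later. Have 6.5.5 and 6.5.6 refer to it.
- In the derivation-table footnote, state that the irPD row is relative to nadir and is applied before the response rows, as 6.5.3 already provides.
- In 6.1, limit the short-axis rule to RECIST 1.1, and record both perpendicular diameters of nodes for irRC.
- Settle this before irRC responses are tabulated.

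The cost is protocol wording and one extra diameter per node, read from scans already taken. No confirmatory scan is added beyond what Table 5 already requires. The irRC response rate may come out slightly lower. The change concerns endpoint classification only.

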7.0 ADVERSE EVENTS

This study will be conducted in compliance with the Data Safety Monitoring Plan (DSMP) of the Robert H. Lurie Comprehensive Cancer Center of Northwestern University (<http://cancer.northwestern.edu/CRO/data/DataandSafetyMonitoringPlanMay2014.pdf>). The level of risk attributed to this study requires high, as outlined in the [DSMP](#). In addition, the study will abide by all safety reporting regulations, as set forth in the Code of Federal Regulations.

7.1 Adverse Event Monitoring

Adverse event data collection and reporting, which are required as part of every clinical trial, are done to ensure the safety of subjects enrolled in the studies as well as those who will enroll in future studies using similar agents. Adverse events are reported in a routine manner at scheduled times during a trial (see Section 5 for time points). In addition, certain adverse events must be reported in an expedited manner to allow for optimal monitoring and patient safety and care.

All patients experiencing an adverse event, regardless of its relationship to study drug, will be followed until:

- the adverse event resolves or the symptoms or signs that constitute the adverse event return to baseline;
- any abnormal laboratory values have returned to baseline;
- there is a satisfactory explanation other than the study drug for the changes observed; or
- death.

7.2 Definitions & Descriptions

7.2.1 Adverse Event

An adverse event (AE) is any untoward medical occurrence in a patient receiving study treatment and which does not necessarily have a causal relationship with this treatment. An AE can therefore be any unfavorable and unintended sign (including an abnormal laboratory finding), symptom, or disease temporally associated with the use of an experimental intervention,

NU Study Number: NU 16G03
Merck Study Number: 3475-244

whether or not related to the intervention.

Any worsening (i.e., any clinically significant adverse change in frequency and/or intensity) of a preexisting condition that is temporally associated with the use of the Merck's product, is also an adverse event.

Changes resulting from normal growth and development that do not vary significantly in frequency or severity from expected levels are not to be considered adverse events. Examples of this may include, but are not limited to, teething, typical crying in infants and children and onset of menses or menopause occurring at a physiologically appropriate time.

Merck product includes any pharmaceutical product, biological product, device, diagnostic agent or protocol-specified procedure, whether investigational (including placebo or active comparator medication) or marketed, manufactured by, licensed by, provided by or distributed by Merck for human use.

All adverse events that occur after the consent form is signed but before treatment allocation/randomization must be reported by the investigator if they cause the subject to be excluded from the trial, or are the result of a protocol-specified intervention, including but not limited to washout or discontinuation of usual therapy, diet, or a procedure.

From the time of treatment allocation/randomization through 30 days following cessation of treatment, all adverse events must be reported by the investigator. Such events will be recorded at each examination on the Adverse Event case report forms/worksheets. The reporting timeframe for adverse events meeting any serious criteria is described in section 7.3. The investigator will make every attempt to follow all subjects with non-serious adverse events for outcome.

Recording of AEs should be done in a concise manner using standard, acceptable medical terms. In general, AEs are not procedures or measurements, but should reflect the reason for the procedure or the diagnosis based on the abnormal measurement. Preexisting conditions that worsen in severity or frequency during the study should also be recorded (a preexisting condition that does not worsen is not an AE). Further, a procedure or surgery is not an AE; rather, the event leading to the procedure or surgery is considered an AE.

If a specific medical diagnosis has been made, that diagnosis or syndrome should be recorded as the AE whenever possible. However, a complete description of the signs, symptoms and investigations which led to the diagnosis should be provided. For example, if clinically significant elevations of liver function tests are known to be secondary to hepatitis, "hepatitis" and not "elevated liver function tests" should be recorded. If the cause is not known, the abnormal test or finding should be recorded as an AE, using appropriate medical terminology (e.g/ thrombocytopenia, peripheral edema, QT prolongation).

Hospitalization for elective surgery or routine clinical procedures that are not the result of an AE (e.g., surgical insertion of central line) need not be considered AEs and should not be recorded as an AE. Disease progression should not be recorded as an AE, unless it is attributable by the site investigator to the study drug.

